## Project Summary

Diet is a cornerstone of type 2 diabetes mellitus (DM2) treatment. Current standard of care diet recommendations focus on caloric restriction and weight loss, goals which can be difficult for patients to achieve. A moderate carbohydrate, high protein diet has been designed specifically for people with DM2, and has shown promising results in preliminary studies. This diet, called the Low Biologically Available Glucose (LoBAG) Diet, does not require caloric restriction or weight loss to produce beneficial effects. Preliminary data are exciting but studies were done only in a small subject population and in a carefully controlled research setting that was not typical of life in the real world. The purpose of this project is to expand upon the preliminary studies and offer the LoBAG diet to a free-living population of people with DM2. In addition, as part of this project, we propose a pilot study to assess the changes in the gut microbiome that occur with this diet in people with DM2.

Subjects with DM2 will be enrolled in a randomized, parallel group trial of the LoBAG diet or a control diet over a 12 week intervention period. The subjects will be free-living and will do food preparation on their own. The main intervention will be instruction in either the LoBAG diet or the control diet. Measures of glycemic control will be collected before, during, and after the diet intervention. Stool samples will be used to collect preliminary data on gut microbiome changes. The diets will be isocaloric and subjects will not be asked to lose weight during the study. Our specific aims include: 1) to determine if the LoBAG diet improves hemoglobin A1c (HgbA1c) in a free-living population with DM2, 2) to investigate the effects of the LoBAG diet on fasting and postprandial glucose and insulin, fructosamine, and lipids, and 3) to determine the effects of the LoBAG diet on the composition of the gut microbiome. The hypothesis to be tested is that the LoBAG diet will produce a significant reduction in HgbA1c when compared to the control diet. The significance of this project will be to expand the generalizability of the LoBAG diet to a free-living population and to potentially improve dietary recommendations for the treatment and control of DM2.

## 1. Background

### 1.1. The LoBAG diet impressively improves glycemic control for subjects with DM2 in a controlled research setting. There remains a crucial need to translate these findings to a free-living population with DM2.

Diet has the potential to be a readily accessible and powerful tool for treatment of DM2. The specific components of the ideal diet, however, have not been clearly defined. According to the American Diabetes Association (ADA), there is no one ideal diet for treatment of DM2, and people with DM2 should focus on an eating pattern rich in nutrient dense foods in appropriate portion sizes (1). For those who are overweight or obese, caloric restriction and weight loss is recommended. Unfortunately, this goal is not usually achieved by patients.

There is both common perception and plentiful evidence that dietary alteration improves glycemic control in DM2 through caloric restriction and weight loss. Yet, studies of a moderate carbohydrate, high protein diet demonstrated impressive improvement in glycemic markers in subjects with DM2 *in the absence of caloric restriction or weight change* (2-5). This diet, the Low Biologically Available Glucose (LoBAGx) diet (subscript indicates percent carbohydrate content in diet), was designed by Nuttall and Gannon for treatment of DM2 (6). The rationale for the design came from two observations made in their previous work: glucose in the diet is the major determinant of postprandial plasma glucose levels, and dietary protein stimulates insulin secretion (6). In a randomized, crossover trial of the LoBAG20 diet (20% carbohydrate, 30% protein, 50% fat) compared to a control diet (55% carbohydrate, 15% protein, 30% fat) in 8 men with untreated DM2, glycated hemoglobin decreased from 9.8 ± 0.5% to 7.6 ± 0.3% (p < 0.001) over 5 weeks. In contrast, there was not a significant change in glycated hemoglobin with the control diet. In addition, both fasting and postprandial plasma glucose decreased with the LoBAG20 diet, as did the net mean 24 hour integrated plasma glucose area response, which decreased by 77%. Subject weight remained stable on both the LoBAG and control diets (3).

Although the LoBAG20 diet was effective, the significant limitation of carbohydrate content compared to a typical American diet was felt to reduce acceptability. Consequently, the LoBAG30 diet (30% carbohydrate, 30% protein, and 40% fat) was designed with a goal of increasing acceptability of the diet for a general population of patients with DM2. The beneficial effect on glycated hemoglobin persisted. In a randomized, crossover trial of the LoBAG30 diet in 8 men with untreated DM2 (2 completed only the test diet period) total glycated hemoglobin decreased from 10.8 ± 0.4% to 9.1 ± 0.5% (p < 0.001) after 5 weeks of the LoBAG30 diet. Weight remained stable. There was a decrease in both fasting and postprandial plasma glucose concentrations with the LoBAG30 diet, and a decrease in 24 hour plasma glucose area response (4). A second study of the LoBAG30 diet in 8 men with untreated DM2 demonstrated that the decrease in glycated hemoglobin continued after 5 weeks, with a decrease in mean glycated hemoglobin from 10.0% at baseline to 8.7% at 5 weeks and 7.5% at 10 weeks (5). A main conclusion from the LoBAG30 studies was that the diet was similarly effective to the LoBAG20 diet in improving glycemic control in subjects with DM2, and contained a carbohydrate content that would be more acceptable to a broad range of patients.

Although these are exciting data, their main limitation was the delivery of the diet in a controlled research setting in a small, all male population. Thus, it remains unknown and is clinically important to determine whether these promising results can be replicated in a free-living population of men and women with DM2.

### 1.2. The gut microbiome may have an important role in the effectiveness of diet therapy for DM2, but its role is not yet understood.

Diet has important effects on the gut microbiome in mice and in healthy human subjects (7-11). It is increasingly recognized that the gut microbiome has a significant role in glucose metabolism (12), and that dysbiosis can lead to perturbations in normal metabolism (13; 14). It has been hypothesized that changes in bacterial metabolites, especially short chain fatty acids and secondary bile acids, is a mechanism by which the microbiome has an effect on metabolism (15-18). In human subjects with DM2, however, there is a knowledge gap. It remains unknown if the dietary recommendations given to patients with DM2 have an effect on the gut microbiome, and if so whether these changes confer metabolic benefit. Since the LoBAG diet alters macronutrient composition of the diet it would be expected to cause changes in the gut microbiome and bacterial metabolites. The importance of this is unknown.

### **1.3. Significance**

The proposed study is significant because it will test the generalizability of the effects of the LoBAG diet in a general population of people with DM2. This could have important implications for DM2 treatment. The study is innovative in its use of a weight neutral, isocaloric, high protein and moderate carbohydrate diet in a free-living population of subjects. There are 29 million people with DM2 in the US (19), and so expanding and improving treatments to maintain glycemic control is an important public health goal. In addition, no study to our knowledge has investigated the gut microbiome before and after a dietary intervention for DM2. By contributing to the limited current knowledge about gut microbiome, diet, and diabetes, the study will provide pilot data for future studies. The study will hope to reshape effective dietary recommendations for the treatment of DM2.

### **2. Hypotheses**

We hypothesize that the LoBAG30 diet will produce a greater reduction in HgbA1c over 12 weeks in a free-living population of subjects with DM2 than a control diet consistent with ADA guidelines, without the need for weight loss. We have an additional exploratory hypothesis that the LoBAG30 diet will induce potential beneficial changes in the gut microbiome, including increased species diversity, increased relative abundance of species associated with a healthy microbiome profile, and increases in short chain fatty acids and secondary bile acids.

### **3. Specific Aims to Test Hypotheses**

#### **3.1. Specific Aim #1: To compare the reduction in HgbA1c over 12 weeks in a free-living population of subjects with DM2 who consume either the LoBAG30 diet or a control diet consistent with ADA guidelines.**

The LoBAG30 diet was chosen for study because of its high level of acceptability to subjects (5) and the likelihood that it could be used by a broad range of patients with DM2. The current ADA diet recommendations were used to develop the control arm of the trial because they represent the current standard of care in diabetes nutrition therapy. We hypothesize that, when compared to a control diet consistent with ADA guidelines, the LoBAG30 diet will produce a better HgbA1c outcome.

#### **3.2. Specific Aim #2: To investigate the effects of the LoBAG30 diet compared to the control diet on fasting and postprandial glucose and insulin, fructosamine, and lipids in a free-living population of subjects with DM2.**

Secondary endpoints to be assessed will include fasting plasma glucose, fasting serum insulin, postprandial glucose response, postprandial insulin response, fructosamine, and fasting serum lipids. It will be important to determine if the LoBAG diet reduces fasting and postprandial plasma glucose and affects serum insulin concentrations in this population. We also want to determine the effect of the LoBAG diet on fructosamine, which is a measure of glycemic control that reaches equilibrium more rapidly than does HgbA1c. Finally, we wish to be sure that the LoBAG diet does not have deleterious effects on the fasting lipid profile.

[figure not shown]

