#### **4.2. Outcome Measures**

The primary endpoint will be HgbA1c at the end of the 12 week diet intervention period. Secondary endpoints will be:

- 1) Weight
- 2) Fasting plasma glucose
- 3) Fasting serum insulin
- 4) Postprandial glucose response at +30, +60, +90, +120, +180 and +240 minutes following the start of a meal consistent with the assigned diet
- 5) Postprandial insulin response at +30, +60, +90, +120, +180 and +240 minutes following the start of a meal consistent with the assigned diet
- 6) Fructosamine
- 7) Fasting serum lipids
- 8) Stool samples for microbiome species analysis. Samples will also be saved for possible bacterial metabolite analysis.
- 9) Glucose variability as measured by continuous glucose monitoring (CGM).

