#### **4.3. Intervention**

A randomized, controlled, parallel group design will be used to compare the effects of the LoBAG30 diet or a balanced diet consistent with current ADA guidelines on our outcomes. Dietary intervention periods will be 12 weeks long. Both the LoBAG and control diets will consist of common foods.

Subjects will be asked to keep their physical activity level constant during the study. Medications for diabetes will be continued without change during the study. Medications will be monitored, and if a participant's medications are altered this will be noted. If antibiotics are used during the study this will be recorded. Subjects will be instructed that they do not need to monitor blood sugars regularly at home.

After enrollment and consent subjects will be randomized in a 1:1 allocation ratio to the LoBAG30 diet or a balanced diet consistent with ADA guidelines. Randomization will be stratified by diabetes treatment at enrollment (no glycemic medications or metformin) and by HgbA1c (7.0-8.5% or 8.5-9.5%), and implemented within stratum using randomly permuted block sizes of 2 and 4. If closely related subjects choose to enroll together (for example spouses or subjects that live together, and would typically share meals) they will be randomized to the same study arm. Baseline measures will be collected. Subjects will meet individually with the study dietitian, who will provide diet instruction, sample menus, and recipes consistent with the assigned diet. Dietitian consultation may be conducted

in person or by phone. During week 2 subjects will have a repeat consult with the dietitian to reinforce diet instruction. If weight has changed caloric intake will be adjusted as necessary for a goal of weight stability. A midpoint visit will be conducted at week 6, during which subjects will provide a blood sample, urine sample, and a stool sample, and will consult with the dietitian for reinforcement of diet advice. If weight has changed caloric intake will be adjusted to prevent further change. Midpoint blood and stool samples will be stored and analyzed in the future based on available funding. At week 9 subjects will consult with the study dietitian for reinforcement of diet advice and collection of a urine sample to assess compliance. The final study visit will be at the end of week 12. All outcome measures will be assessed at the final visit.

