#### **4.7. Methods of Data Analysis**

The primary outcome will be HgbA1c at the end of the 12-week study period. Results will be compared pre and post diet intervention (within an individual subject) using paired t-tests and between dietary interventions (LoBAG30 versus control) using unpaired t-tests. Data will be analyzed at study completion.

Sample size was estimated a priori based on a two-tailed type I error of 0.05. For a difference of 1.5 points in HgbA1c and a power of 80%, 12 participants are required per intervention group. This number was increased by 30% to account for participant loss during screening, and an additional 30% to account for participant attrition, yielding 19 participants per intervention group (total 38 participants). An additional 12 participants have been enrolled using pilot funding from the University of Minnesota (of which 8 were eligible and 6 completed the entire study intervention).

This estimate uses preliminary data from existing LoBAG30 studies which were collected in a carefully controlled research setting. This differs from the conditions planned for this study. There are no data on the performance of the LoBAG30 diet in a free-living population of subjects with DM2. Thus, we will generate data that can be used to estimate effect size and variability for a power calculation for a future larger clinical trial.

With a goal of 38 plus 6 subjects completing the entire 12-week intervention, we anticipate recruiting up to 70 subjects in total.

If a subject withdraws from the study prior to study completion they will be invited to complete the final study visit prior to withdrawal, if possible. Any data collected from the subject prior to study withdrawal will be included in the final analysis. In the case of subject withdrawal an additional subject will be recruited to replace accordingly, dependent on funding.

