**NCC Diet Recall**

- If funding allows, telephone call conducted by the Nutrition Coordinating Center (NCC) for an unannounced 24 hour diet recall (30 minutes; prior to visit 2/diet start).

**Visit 2.** Diet Instruction and Baseline Labs. (5 hours; beginning of Week 1)

- Subjects bring in stool sample or return by mail.
- If applicable, subjects bring in CGM sensor or return by mail.
- Collect weight, height, blood pressure.
- Fasting blood draw (for plasma glucose, serum insulin, lipid panel, fructosamine, and a stored sample).
- Provide a test meal consistent with the assigned diet (Control diet arm: 50% carbohydrate, 15% protein, 35% fat or LoBAG30 diet arm: 30% carbohydrate, 30% protein, 40% fat). The composition of the control diet was chosen to be consistent with typical macronutrient intake in the United States (21) and consistent with ADA guidelines (1). In addition to the fasting samples, obtain plasma glucose and serum insulin at +30, +60, +90, +120, +180 and +240 minutes following the start of the meal.
- Collect 3-day food diary.
- Collect list of current medications.
- Collect baseline compliance survey, Diet Satisfaction Questionnaire, and Diabetes Treatment Satisfaction Questionnaire if not already administered at Visit 1.
- Meeting with study dietitian for diet instruction. Sample menus and recipes consistent with the assigned diet will be provided. Dietitian consult may be conducted by phone if needed to facilitate scheduling.
- If funding allows, provide Actigraph Activity Monitor for subject to wear between Visits 2 and Visit 3.

**Visit 3.** Diet Reinforcement. (1 hour; Week 2)

- If applicable, subjects return Actigraph Activity Monitor.
- Measure weight.

- Collect urine sample for urine nitrogen and urine creatinine.
- Meeting with study dietitian for reinforcement of diet advice. Adjust caloric intake if needed for goal of weight stability. Dietitian consult may be conducted by phone. If dietitian consult is conducted by phone the participant will be encouraged, but not required, to come to the study center for weight and urine sample collection (this exception applies to visit 3 only).

**Visit 3.1.** (5-10 minutes; Week 4)

- Telephone call conducted by study investigator or coordinator to encourage study compliance.

**Visit 4.** Midpoint Visit. (1 hour; Week 6)

- Subjects bring in stool sample or return by mail.
- Measure weight and blood pressure.

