**NCC Diet Recall**

- If funding allows, telephone call conducted by the Nutrition Coordinating Center (NCC) for an unannounced 24 hour diet recall (30 minutes; Week 9-12).

**Visit 6.** Final Visit (5 hours; end of Week 12)

- Subjects bring in stool sample or return by mail.
- If applicable, subjects return Actigraph Activity Monitor.
- If applicable, subjects bring in CGM sensor or return by mail.
- Collect weight and blood pressure.
- Collect urine sample for urine nitrogen and urine creatinine.
- Fasting blood draw (for HgbA1c, plasma glucose, serum insulin, lipid panel, fructosamine, and a stored sample).
- Provide a test meal consistent with the assigned diet (Control diet arm: 50% carbohydrate, 15% protein, 35% fat or LoBAG30 diet arm: 30% carbohydrate, 30% protein, 40% fat). In addition to the fasting samples, obtain plasma glucose and serum insulin at +30, +60, +90, +120, +180 and +240 minutes following the start of the meal.
- Collect 3-day food diary.

- Collect list of current medications.
- Collect end of study compliance survey, Diet Satisfaction Questionnaire, and Diabetes Treatment Satisfaction Questionnaire.
- Meeting with study dietitian for debriefing and dietary advice for after study completion. Dietitian consult may be conducted by phone.

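### Aim 2 seeks assurance that LoBAG30 does not harm fasting lipids, but difference t-tests at about 22 per arm cannot exclude a moderate harmful effect; restate the lipid objective as estimation with a confidence interval

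*Combined protocol and SAP*

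**What the plan says.** Section 3.2 closes its account of the secondary endpoints with a statement of intent on lipids: "we wish to be sure that the LoBAG diet does not have deleterious effects on the fasting lipid profile". Section 4.2 lists the endpoint only as "Fasting serum lipids", one of nine secondary endpoints. No lipid fraction is named and no deleterious change is defined.

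Lipids are measured twice. Appendix 1, Visit 2 has "Fasting blood draw (for plasma glucose, serum insulin, lipid panel, fructosamine, and a stored sample"; Visit 6 has "Fasting blood draw (for HgbA1c, plasma glucose, serum insulin, lipid panel, fructosamine, and a stored sample".

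Section 4.7 names HgbA1c as the primary outcome and then describes the analysis in general terms: "Results will be compared pre and post diet intervention (within an individual subject) using paired t-tests", and LoBAG30 "versus control) using unpaired t-tests". It does not assign an analysis to lipids explicitly, does not say whether the between-arm test uses the change or the final value, and gives no margin, interval criterion or lipid sample size.

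On drugs, Section 4.3 says "Medications for diabetes will be continued without change during the study". It adds that medications are monitored and alterations noted. Appendix 1 collects medication lists at Visits 2, 4 and 6; under Appendix 2 the baseline list is taken at Visit 1. No rule says how a change in lipid-lowering treatment enters the analysis.

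**The concern.** Assurance of no harm and a test of no difference are different tasks. The first needs the data to rule out a harmful difference. The second can fail to reject simply because the trial is small. Neither planned t-test, read as significant or not, supplies what the sentence in Section 3.2 asks for. The paired test has the further limit that it is not a randomised comparison.

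The question is a natural one for this diet: by the compositions in Appendix 1, LoBAG30 supplies 40% of energy as fat against 35% in the control diet. The project also hopes to inform dietary recommendations. If a non-significant lipid comparison were taken as evidence of safety, the reassurance would be unfounded, and nothing in the plan guards against that reading.

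**Working it through.** **Inputs from the documents.** Two-sided alpha 0.05 (Section 4.7, stated for HgbA1c); 1:1 allocation (Section 4.3); goal of 38 + 6 = 44 completers (Section 4.7), so 44 / 2 = 22 per arm.

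**Input not in the documents.** The SD of the lipid measure. Results are therefore in units of that SD, meaning the SD of whatever quantity is compared (change, or week-12 value adjusted for baseline). Participants are treated as independent.

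**The plan's own figure.** Section 4.7 gives 12 per group for a 1.5-point HgbA1c difference at 80% power, without an SD, so it cannot be reproduced directly. Back-solved with the normal formula, SD = 1.5 / [(1.960 + 0.842) × √(2/12)] = 1.31; with the t distribution it is 1.25. The inflation reproduces as 12 × (1 + 0.30 + 0.30) = 19.2, or 19 per group. None of this concerns lipids.

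**Precision of the between-arm lipid difference.** Half-width of the 95% CI = t(0.975, 42) × √(2/22) × SD = 2.018 × 0.3015 × SD = 0.61 SD. An observed difference of zero leaves harm up to 0.61 SD open. An unfavourable difference just short of significance has its upper limit near 0.61 + 0.61 = 1.22 SD.

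**Power of the unpaired test.** Noncentral t, 42 degrees of freedom, noncentrality d × √(22/2), where d is the true rise in SD units:

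| True rise | Power | Missed |
|---|---|---|
| 0.3 SD | 16% | 84% |
| 0.5 SD | 37% | 63% |
| 0.6 SD | 49% | 51% |
| 0.8 SD | 74% | 26% |
| 1.0 SD | 90% | 10% |

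Power reaches 50% at 0.60 SD and 80% at 0.86 SD.

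**Excluding harm formally.** With a true difference of zero, one-sided 0.025 and 80% power, n per arm = 2 × (1.960 + 0.842)² / m² for a margin of m SD. This gives 63 for m = 0.5, 25 for m = 0.8 and 22 for m = 0.85. With 22 per arm and m = 0.5, the power to exclude harm is Φ(0.5 × √11 − 1.96) = 38%.

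**Illustration in mg/dL.** Assumed SDs of 20, 25 and 30 mg/dL, not taken from the documents:

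| | SD 20 | SD 25 | SD 30 |
|---|---|---|---|
| 95% CI half-width, mg/dL | 12.2 | 15.2 | 18.3 |
| Power, rise of 10 | 37% | 25% | 19% |
| Power, rise of 15 | 68% | 49% | 37% |
| Power, rise of 20 | 90% | 74% | 58% |

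**The case against.** The strongest reply is that this is a loosely worded sentence, not a formal objective. The heading of Aim 2 is to investigate effects, Section 2 states no lipid hypothesis, and Section 4.7 says openly that the trial will generate effect sizes and variability for a larger study. That stands, and it limits how much weight the point carries. It does not remove the mismatch: the sentence is still there, and a trial meant to estimate effects is better served by an interval than by a test.

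A reader might infer more than the documents support, in four ways:

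- **That a clinically important rise would usually be missed.** The documents give neither a lipid SD nor a definition of an important rise. Missing is more likely than not only below about 0.6 SD. At the assumed SDs, a 20 mg/dL rise is detected 58% to 90% of the time.
- **That the between-arm test is the only one planned.** The paired test within the LoBAG30 arm, with 22 participants and the same assumed SDs for the change, would flag a 15 mg/dL rise with 61% to 92% power. It cannot separate diet from other changes over time, and it does not exclude harm, but a rise could well be noticed.
- **That the trial will report no lipid effect.** Nothing in the plan says how a non-significant lipid result will be read.
- **That lipid-lowering drug changes are ignored.** They are recorded at several visits. Only a rule for using the records is missing, and nothing in the documents suggests that such changes will be frequent or unequal between arms.

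**Conclusion.** The point holds as a mismatch between a stated wish and the method offered. Whatever the lipid SD, a non-significant t-test does not show absence of harm. At 22 per arm, the interval is about 0.61 SD either side of the estimate, and the trial could exclude with 80% power only a harm of about 0.85 SD or more.

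The SD-unit figures rest on 44 completers split evenly, independent participants and a two-sided 5% level. With 19 per arm the half-width would be 0.66 SD. The mg/dL figures rest on assumed SDs and should not be quoted as properties of this trial.

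This is a cheap improvement to a secondary objective. It does not affect the primary comparison, and it does not show that the trial will give false reassurance.

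**What to change.** In Sections 3.2 and 4.7:

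1. Restate the lipid objective as estimating the effect of LoBAG30 relative to control on each fasting lipid.
2. Name the lipid fractions. For each, report the between-arm difference at week 12, adjusted for the Visit 2 value, with a 95% confidence interval.
3. State that a non-significant difference will not be read as no deleterious effect, and that harm up to the upper confidence limit is not excluded (the lower limit for a fraction where a fall is the harm).
4. Keep all participants with lipid data in this comparison, whatever happened to their medication. Report starts and changes of lipid-lowering drugs by arm from baseline to Visit 6, using the lists already collected (baseline being Visit 1 where Appendix 2 applies).

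Item 4 is deliberately not an analysis that drops participants whose lipid-lowering drug changed. That would be an exclusion after randomisation. If a diet-related rise prompted the change, it would remove the very people harmed and tilt the result towards reassurance.

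The cost is a few sentences, one regression per lipid and one small table. No visits, samples or participants are added. The downside is that the trial will probably have to report that a modest adverse lipid effect is not excluded.
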